6.1.1.9 ANCILLARY PRODUCTS AND ACCESSORIES

During Visit 0, Participants will be provided with diabetes diaries and a bag of material for times spent at home in between study visits to the CRU.

Contents of bag:

- Achilles infusion set change out and device return instructions
- Glucose meter (handling is explained by study staff)
- Ketone meter (handling is explained by study staff)
- Glucose strips
- Ketone strips
- Glucose tabs
- Diary

- Cap for infusion set (in case of failure)
- Ruler/Cutout to measure erythema
- Container & biohazard bag for CSII catheter (in case of failure)
- Alcohol swabs

Study sponsor shall provide the following study materials and products for study use only:

- Dexcom G6® CGM
- Fast-acting insulin (Insulin Lispro U100/Humalog)
 - **NOTE:** Participants who are using other pump insulins will be switched to lispro after screening and informed consent to participate have been completed.

6.1.9 STUDY VISIT WINDOWS

Study visits are scheduled as indicated above; however, it is recognized that study participants may not be able to return for scheduled visits at precisely the date required. Therefore, study visit windows have been defined for each visit per Table 8 below.

Table 8: Schedule of Follow-Up Visits and Visit Windows

Visit	Visit Window
Screening/Baseline	-28 to -1 days
Wear Period	DOI to +7 days inclusive
Study Completion	8 th calendar day or upon infusion set failure
Follow-up	Patients will receive follow-up phone call by staff 1 day after each period

6.2 PREPARATION/HANDLING/STORAGE/ACCOUNTABILITY

Sterile study devices (Achilles infusion sets) shall be provided by the Sponsor and stored in a cool, dry, secure location at each study site. Insulin lispro shall be stored and dispensed per site requirements. Study BG and ketone monitors, test strips and study CGMs shall be stored per the labeling. All ancillary study products will be labeled and distributed to the sites to be provided to each study participant on Day of Insertion (Day 0). All study device and drug inventory must be returned to the study center or pharmacy before the participant officially exits the study.

6.2.1 FORMULATION, APPEARANCE, PACKAGING, AND LABELING

Achilles infusion sets come packaged sterile and single use only in a Tyvek pouch. Sufficient quantities of investigational infusion sets will be provided to the study center prior to study start. Replacement and/or additional units shall be provided upon site request to Sponsor.

Insulin lispro will be provided per standard packaging and labeling by the affiliated study center pharmacy. Insulin will be dispensed per the study protocol and only for the study duration to any eligible study participant.

6.2.2 PREPARATION

Achilles infusion sets shall be prepared and applied to the participant as described in reference document “710-1021-00 Achilles infusion set, Instructions for Clinical Use”. For this 7-day study, 23” (60 cm) tubing from commercially-available MiniMed Silhouette infusion sets shall be used.

The infusion set hub shall be secured to the body with a kinesiology tape over-bandage. If the participant routinely under-bandages or over-bandages using other dressings with their normal infusion set they should continue to do so when using the Achilles infusion set.

Insulin lispro, infusion pump, BG and ketone monitors and study CGM shall be prepared per the applicable product instructions for use. IV insulin will be prepared by the investigational site pharmacy or equivalent. Insulin reservoirs are filled with insulin lispro and inserted into the participant’s pump on Visit 1 or other clamp days (depending on the participant’s insulin requirements, 1 reservoir may last the entire treatment period or less).

6.2.3 ACHILLES INFUSION SET DEVICE ACCOUNTABILITY

The Sponsor shall keep records to document the physical location of all investigational devices from shipment of investigational devices to the investigation sites until return or disposal. The principal investigator or an authorized designee shall keep records documenting the receipt, use, return and disposal of the investigational devices, which shall include the date of device receipt, investigational device identification (batch, serial or unique study ID code), expiry date if applicable, date or date(s) of use, related participant study ID, data device was returned/removed from participant, date of return of unused or expired device inventory. Product accountability returns and/or exchanges shall be documented per Sponsor standard operating procedures and investigational product release and return procedures.

Ancillary products shall be labeled with the participant’s study ID number. Records of study provided glucose and blood ketone monitors and CGM will be tracked as required above. Insulin will be dispensed per pharmacy standard operating procedures to study participants only.

6.3 MEASURES TO MINIMIZE BIAS

Participant treatment will be assigned in a randomized sequence to avoid sequence bias. A washout period of 2±1 week will be used to avoid treatment bias.

6.4 STUDY COMPLIANCE

Study compliance will be assessed during the initial participant instruction period, and by review of daily diary and Dexcom G6 app entries. The investigational device will be applied to the study participant only after the participant has demonstrated an understanding of the study instructions, change out activities, the need to complete all study test requirements as written. If the study staff become aware of participant non-compliance to protocol requirements or follow-up evaluations, multiple attempts will be made to contact the participant to ensure patient safety and protocol adherence.

Adherence to glucose test procedure will be assessed by study personnel at site. All CRFs must be completed and CGM data will serve as electronic source documentation for hyperglycemic and hypoglycemic adverse events. Additionally, inquiries documented in clinic notes will be used for source documentation of patient-reported AEs. Photographs of infusion site will serve as source documentation for infusion site reactions.

The following will be collected regularly and documented:

- Study participant's insulin pump records
- Interstitial fluid glucose data from Dexcom G6® CGM throughout each study period (assessed by study staff at each study visit)
- BG measurements per Bayer Contour NEXT device will be used by participants for SMBG data collection as mandated by protocol requirements. Data will be downloaded at each clinic visit
- Serum ketones - measured by Abbott Precision Xtra Ketone meter (in case of hyperglycemia occurring during fasting or acute illness)
- Study participant diary (Pain score, SMBG)

6.5 CONCOMITANT THERAPY

The use of concomitant medications is permitted with the exception of non-selective beta-blockers that may mask the symptoms of hypoglycemia and analgesics such as acetaminophen taken 12 hours prior to a pain assessment to minimize the risk of confounding VAS scores.

6.5.1 RESCUE MEDICINE

Standard of care rescue medicine will be allowed to treat:

- Transient hyperglycemia (insulin using commercial CSII cannula)
- Transient hypoglycemia (juice or glucose tabs or, as needed, glucagon or IV glucose)

7 DISCONTINUATION AND WITHDRAWAL

7.1 DISCONTINUATION OF STUDY INTERVENTION

7.1.1 INFUSION SET CHANGE-OUT/EARLY DROPOUT

Independent of the time point for infusion set removal/change out, study staff is to follow the SOP for Infusion Set Removal and the reason for change-out is to be documented in the applicable source document and CRF.

We anticipate several commercial and/or investigational CSII catheters to fail prior to the fourth glucose clamp experiment on day 7. Participants will be instructed to contact the research investigator by telephone (24/7) to confirm the diagnosis of a failed CSII catheter. If the CSII catheter does not fail before day 7, the investigational/commercial CSII set will be removed upon completion of the clamp experiment on Visit 4A/Visit 4B. The site and cannula will be photographed, and the cannula inspected under a microscope.

The following are objective criteria that define a CSII catheter/infusion set failure:

1. The occurrence hyperglycemia (glucose >250 mg/dL) not responsive to a pump bolus dose where response to the bolus is defined as a fall of at least 50 mg/dL in blood glucose within one hour.
2. The occurrence of hyperglycemia (glucose >250 mg/dL) after prolonged fasting (e.g. overnight or more than 5 hours following a meal), not associated with acute intercurrent illness, but with a concurrent ketone level ≥ 0.6 mmol/L.
3. Signs of inflammation/infection at the infusion site including pain, erythema or induration >10 mm in diameter.
4. Occurrence of an insulin pump occlusion alarm signal.

In the case that any of the above occurs during home-use, the participant is asked to call the 24/7 helpline and confirm catheter failure with the study staff. The study participant will insert a new commercial CSII catheter (as used routinely by this patient) into the subcutaneous tissue at an alternate location and connect it to the insulin pump for routine glycemic management. The failed CSII catheter will be left in place. The participant is asked to measure erythema around the catheter and photograph the site. The study participant will return to the study site as soon as practicable so the research staff can remove and observe the failed CSII catheter. Study staff is to follow the SOP for catheter removal.

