
Description of Study Intervention:
	
Existing patient populations at each study center will be screened for study eligibility within 28 days of planned study enrollment. Participants without prior experience using the Dexcom G6 will be allowed up to 14 days of a run-in period to familiarize themselves with the CGM device. Eligible participants will complete written informed consent and be assigned a unique study ID.
 
Eligible participants will be randomized for Treatment Period A to either the Achilles investigational cannula or a Medtronic Silhouette control cannula using commercially available tubing, insulin lispro, insulin pumps and continuous glucose monitoring (CGM) equipment. After 2±1 week of washout each participant will enter Treatment Period B for a second 7-day period of catheter wear-time using the other infusion set.
 
On Day of Insertion (Day 0), participants will have the investigational Achilles infusion set or the control infusion set inserted by a qualified professional during a clinic visit. Participants will undergo training and be provided written instructions if infusion set change out is required during the 7-day wear period.
 
At the start of the study, participants will be provided with an insulin lispro vial (Humalog®, Eli Lilly and Co., Indianapolis, IN), a 23” tubing set compatible with the Achilles infusion set and Ascencia Contour Next glucose monitor plus test strips. Participants will also wear a study-provided Dexcom G6® (study continuous glucose monitor, to be used in real time mode) for the duration of the study. Participants will manage routine basal/bolus insulin therapy using these supplies and their current insulin pump for two home use wear periods of up to 7 days each. Finally, an Abbott Precision Xtra ketone monitor plus test strips will be provided for use in the event of hyperglycemia >250 mg/dL.
 
Visual inspection and photographic documentation of the Achilles and the comparator infusion set insertion site will be recorded at Day 0. Participants will be asked to conduct daily insertion site visual inspection and report/record site reactions, glycemic intervals and/or the need for infusion set change out (Days +1 to +7).
 
During a 7-day wear period, participants will undergo 4 in clinic euglycemic glucose clamps [Day of Insertion (DOI) and 3, 5, and 7 days later] to assess pharmacokinetics (PK) and pharmacodynamics (PD) of a bolus of lispro insulin (0.15 U/kg) when delivered using an insulin pump.
 
Upon completion of the first wear period (after 7 days or sooner, in the event that infusion set change out has occurred) and a 7-21 day washout period, participants will return to the investigational clinic site and will have a second infusion set inserted by a qualified professional. Sequence of control and investigational infusion set will be randomized.
 
It is expected that infusion set change out may be required prior to the end of the 7 day wear period. If necessary, participants will follow written instructions for change out to a commercial CSII set and return to the study center for visual and photographic evaluation of the insertion site. CGM data will be available to the study site in real time (and will be reviewed at each clinic visit) by using Dexcom Clarity software to access the individual participant’s Dexcom cloud account data. Data will be downloaded from the participant’s

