2.3.3 RISK BENEFIT ANALYSIS

This study includes T1DM participants who undergo routine diabetes treatment and glucose control methodology. A standardized study protocol, case report forms, study and investigational device use training will be provided to all study investigators/staff and study participants prior to any study related intervention or testing.

The study population consists of adult volunteer participants who have been diagnosed with T1DM, and have used an insulin pump for at least 6 months for basal and bolus insulin therapy to control their blood glucose. T1DM diagnosis will be confirmed at screening by c-peptide lab test.

Only insulin pump users with at least 6 months of experience with pump therapy will be enrolled to minimize the risk of pump use errors. Each potential study participant will be required to submit a minimum of 14 days of pump data to confirm pump use compliance. Patients who routinely wear their infusion set for > 4.5 days will be excluded from participation to ensure a homogenous patient population of participants who adhere to infusion set labeling restrictions. Screening including physical exam, ECG and laboratory testing will rule out patients with anemia or known cardiovascular disease who may be at greater risk of procedure-induced anemia or whose hypoglycemia symptoms may be masked by concomitant medication.

The primary risks associated with extended wear of the Achilles infusion set are increased risk of hyperglycemic or hypoglycemic episodes and/or infusion site irritation or infection. To ensure patient safety while using the newly developed infusion sets, patients are required to wear a CGM sensor throughout the study. Only patients with at least 3 months of CGM experience will be recruited. The personal CGM should be set with alarm systems engaged throughout study duration. Study staff will be able to monitor each patient's interstitial glucose remotely and will be notified via text in case of alarm. Participants will be instructed to contact their study site for any issues.

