4.1 OVERALL DESIGN

This is an open, single-center, 2-way randomized, cross-over trial investigating the survivability, consistency, efficacy, and safety of an extended wear time investigational insulin infusion set (CapBio Achilles). This is achieved by measuring PK and PD profiles of a bolus of rapid acting insulin on 4 separate days of CSII set wear time during 2 separate wear periods in up to 30 adult patients with T1DM.

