4.3.3 Safety Variables

4.3.3.1 Device Malfunctions

4.3.3.1.1 Hyperglycemia (Glucose >250 mg/dL) not Responsive to Correction Bolus

This hyperglycemia episode is reported by the investigational site. Occurrence of these cases will be counted. A subject without any reported cases will have a count of 0.

4.3.3.1.2 Hyperglycemia with Elevated Ketones (Glucose >250 mg/dL and a Ketone Value ≥ 0.6 mMol/L) in the Absence of Evidence of Intercurrent Illness.

This hyperglycemia episode is reported by the investigational site. Occurrence of these cases will be counted. A subject without any reported cases will have a count of 0.

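### Failure-type events come from unmasked site reports, no report is scored 0, and the SAP has no cross-check against the CGM and pump records already collected

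*Protocol*

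**What the plan says.** Protocol 4.1 describes the study as open: "This is an open, single-center, 2-way randomized, cross-over trial". Protocol 7.1.1 lists four failure criteria. For the first, unresponsive hyperglycemia, "response to the bolus is defined as a fall of at least 50 mg/dL in blood glucose within one hour". If any criterion is met at home, "the participant is asked to call the 24/7 helpline and confirm catheter failure with the study staff".

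SAP 4.3.3.1.1 and 4.3.3.1.2 cover unresponsive hyperglycemia and hyperglycemia with raised ketones. For each, "This hyperglycemia episode is reported by the investigational site", and "A subject without any reported cases will have a count of 0". SAP 4.3.3.1.3 to 4.3.3.1.5 apply the same rule to infection or inflammation, dislodgement and other malfunctions.

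SAP 4.3.2.7.1 defines set failure in words and divides the sets that have not failed by the sets inserted. It gives no data source. SAP 4.3.2.7.3 and 4.3.2.7.4 count occlusion alarms per day, with neither a site-report rule nor a zero default.

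On data, Protocol 6.4 states that "CGM data will serve as electronic source documentation for hyperglycemic and hypoglycemic adverse events" and lists pump records among the items collected. Protocol Table 2 has pump and SMBG downloads at every clamp visit. The SAP uses CGM only for daily mean, SD, CV and time in range (SAP 4.3.2.6).

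**The concern.** The participant and the site staff both know which set is in place. If they are readier to call a failure on one set than on the other, the difference passes directly into the comparison of failure counts and survival. An episode that meets the first criterion on the glucose trace and bolus log, but that nobody reports, leaves no mark on the safety count. It probably leaves none on survival either, because the survival section has no other stated source.

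The zero rule adds a second problem. It is written per subject and does not depend on data being available, while summaries are by treatment and period (SAP 4.4.2). Taken literally, a wear with no usable records, or one that never took place, is scored as free of events.

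The failure rate carries weight. It is a secondary endpoint in the protocol synopsis and the measure named in the safety objective (Protocol 3.3). SAP 4.4.4.1 calls it the primary endpoint, although the protocol gives that place to the slope of log AUC.

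**Working it through.** The plan states no figure on this point, so there is none to reproduce. The check has two parts.

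**Tracing detection to counting**

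| Route to an event | Where | Tied to the count? |
|---|---|---|
| Helpline call, staff confirm | Protocol 7.1.1 | Not explicitly |
| Staff watch glucose remotely and "will be notified via text in case of alarm" | Protocol 2.3.3 | No; no alarm threshold given |
| CGM reviewed at clinic visits | Protocol 1.1 | No |
| Pump and SMBG downloads; set problems recorded | Protocol Table 2 | No |
| Daily diary, including set failure | Protocol 6.1.1.7, Table 7 | No |
| Staff determination during a clamp | Protocol 6.1.1.5 | No |
| Site report | SAP 4.3.3.1 | Yes, for the safety counts |

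Every route reaches the safety counts only through the site's decision to report. No step compares those reports with the logs.

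The two failure definitions also differ. Protocol 7.1.1 gives numeric thresholds and counts any occlusion alarm. SAP 4.3.2.7.1 gives no thresholds and requires the alarm to be non-resolvable. Protocol 7.1.1 refers to a pump bolus, the SAP to a correction bolus. The 50 mg/dL response rule does not appear in the SAP.

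**Scale, for illustration only**

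Neither document gives a reporting probability, so these are assumed. Suppose both sets truly fail at rate *p*, and the reported share of failures differs by *d* between them. The spurious difference is *p* × *d*.

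| Base rate *p* | Source | *d* = 0.10 | *d* = 0.20 | *d* = 0.30 |
|---|---|---|---|---|
| 0.30, hyperglycemia with failed correction, steel and Teflon pooled | Protocol 2.2.3 | 3 points | 6 | 9 |
| 0.15, Teflon, after the first hours | Protocol 2.3.3 | 1.5 | 3 | 4.5 |
| 0.40 to 0.50, all failures | Protocol 9.4.1 | 4 to 5 | 8 to 10 | 12 to 15 |

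The last row assumes that the gap applies to every type of failure, so it is an outer case.

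In events, suppose one set's failures are fully reported and the other's at 70%. Of 24 wears, 24 × 0.40 × 0.30 = 2.9 to 24 × 0.50 × 0.30 = 3.6 failures are missed. Of 7 wears, 0.8 to 1.1 are missed.

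SAP 2.5 says the study was stopped after the seventh subject completed. With seven wears per set, one missed failure moves that set's rate by 1/7 = 14.3 points. At the planned 24 it would be 1/24 = 4.2 points.

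**The case against.** The site is well placed to find events without a call. It has remote alarms, CGM review, downloads, diaries and a staff call on the evening after the clamp. The visit schedule is written by visit and period, not by device, and sequence is randomized, so the same procedures apply to both sets. Any switch to another set counts as removal (SAP 4.2.6). The safety counts are only described, not tested (SAP 4.4.5.4). With about seven wears per set, even a 9-point bias is 7 × 0.09 = 0.6 of one event.

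Most of this stands, and it rules out three stronger readings that a reader might infer:

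- **That events count only if the participant calls.** No passage makes counting depend on a call, and the other routes are documented.
- **That the zero default governs set survival or alarm counts.** It is written only for the safety counts in SAP 4.3.3.1.
- **That the two sets are screened by different procedures.** The schedule gives no support for this. What is missing is a common rule for turning the collected data into events.

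A log-based rule also has limits. One that accepted any logged bolus would flag ordinary meal excursions, and automatic-mode pumps are allowed (Protocol 5.2). The logs cannot settle the ketone criterion, which also needs fasting and illness information, or the site-reaction criterion, which needs inspection.

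The objection does not remove the gap. Equal procedures do not ensure equal reporting by people who know the device, and the plan has no means of seeing a difference. SAP 4.2.6 records that a set was removed. It does not find a set that met a criterion and stayed in use.

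**Conclusion.** The point holds as a gap in ascertainment and verification. In an open trial, failure-type safety events rest on site reports, absence of a report is scored 0 without regard to available data, survival has no stated source, and the collected logs are not used as a check.

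The documents do not show that reporting differs between sets, or in which direction. The 3-to-9-point range depends on assumed reporting gaps and on a 30% figure that pools steel and Teflon sets; on the roughly 15% Teflon figure it is 1.5 to 4.5 points. The figure of about 14 points per missed failure assumes seven wears per set and no additional partial participants in the denominator. This is an inexpensive improvement to the analysis, not a defect that invalidates the comparison.

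**What to change.** 1. **Reconcile the failure definitions** in Protocol 7.1.1 and SAP 4.3.2.7.1 (thresholds, type of bolus, which occlusion alarms count), and name the data source for survival.
2. **Add a sensitivity analysis** to SAP 4.3.2.7.1 and 4.3.3.1.1, run by one program for both sets while the study set is in place. If the Protocol 7.1.1 thresholds stand, flag CGM or SMBG glucose above 250 mg/dL followed by a logged correction bolus and a fall of less than 50 mg/dL within 60 minutes. Exclude meal boluses and automatic-mode deliveries. Use recorded readings, not the spline-filled values that SAP 4.3.2.6.1 allows for gaps of up to 2 hours. Take occlusion alarms from the pump log.
3. **Report both versions** of counts and survival side by side, site-reported and log-derived, and list the discordant episodes.
4. **Make the zero conditional** in SAP 4.3.3.1: score 0 only for a wear that took place and has data available; otherwise set it to missing.
5. **Leave the ketone and site-reaction criteria site-reported.**

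The cost is SAP wording and some programming on data already collected, for about 14 wears if seven participants each wore both sets. CGM is not blood glucose, so some flags will be false. The derived count should therefore stand beside the site-reported one and not replace it.

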³ Vital signs include BP (seated or recumbent), pulse, respiratory rate and temperature; VS should be done every 2 hours ± 30 min during clamp procedures

⁴ Ascensia Contour Next glucose monitor and Precision Xtra blood ketone monitor with respective test strips will be provided.

⁵ 100 mm Visual Analog Scale (VAS) pain assessment to be performed at Achilles infusion set insertion, daily during home wear period, and at time of Achilles infusion set removal.

⁶ End-of-Study (EOS) and Early Termination (ET) Assessments; if participant terminates early because of cannula failure event then glucose clamp will not be done if failed cannula has been removed. Study completion time may differ per participant. Study is considered complete at the end of the second wear period as determined by: **(1) Participant has worn Achilles infusion sets for 7 days, (2) Participant experiences Achilles set failure requiring change out to commercial CSII set, (3) Participant has hyperglycemic event requiring at home change out to commercial CSII set, or (4) Resolution of device or procedure-related AEs.**

⁷ Blood for clamping decisions every 5-15 min for 300 min

⁸ Meal and individually determined bolus dose of insulin delivered via pump bolus performed in clinic; participants may be discharged home shortly after meal is completed. The same meal and insulin bolus dose (unless clinically indicated that bolus dose should be modified) to be provided for each participant after all clamp studies

⁹ Insertion Site Evaluations for each wear period: Day 0 pre-infusion set insertion and after securing post-insertion; Daily during Day 0 to +7 wear period; Day 7 (or upon infusion set failure) pre-infusion set removal, post-infusion set removal. The site personnel will perform photographic documentation of the insertion site at the time of insertion and at the time of presentation to the study site at the end of each wear period.

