Commercial subcutaneous insulin infusion sets have a known failure rate of approximately 15 - 25% prior to their labelled 3 day (72 hour) wear duration. Therefore, T1DM patients are accustomed to frequent change outs with commercial infusion sets. In response to these known issues, the Capillary Biomedical Achilles infusion set incorporates a kink-resistant coil-reinforced soft polymer cannula. This cannula contains one distal and three proximal holes to ensure redundancy and extended wear-time of up to 7 days.

Failure of the investigational Achilles infusion set may occur during the 7 day extended wear period. However, if Achilles infusion set failure occurs at any time during the home wear period, the participant will simply be instructed to change out the investigational device for their standard commercially available set to maintain CSII therapy. This is the same risk associated with a use of commercially available infusion sets.

CSII set infusion site irritation and infection are familiar risks to insulin pump users. The investigational Achilles infusion set will be manually inserted and secured (taped) to an appropriately selected body location by a trained study staff member. Participants will be observed at the study center for 3 hours to ensure initial Achilles infusion set function prior to clinic discharge and start of home-use period. Study staff may attempt infusion set insertion three times. If insertion is not successful after 3 attempts, the Achilles infusion set is considered failed for this study participant.

Study participants will be instructed to check the infusion site for any skin abnormalities on a daily basis. All findings of skin irritation/infection (including tape reactions or cannula dislodgement) will be carefully monitored and recorded in a participant diary. If there is evidence of an infection at the infusion site, participants will be instructed to remove the infusion set and insert a fresh insulin infusion set as per their clinical routine. The Achilles infusion set will be placed in a provided container and biohazard bag. Participants are instructed to photograph the inflamed infusion site and contact the study staff via the provided study hotline.

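### For a suspected infusion-site infection at home, Protocol 2.3.3 has the participant take the set out, Protocol 7.1.1 leaves it in until staff remove it, and neither is given precedence.

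*Protocol*

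**What the plan says.** Protocol 2.3.3, in the risk-benefit case, tells the participant what to do about infection: "If there is evidence of an infection at the infusion site, participants will be instructed to remove the infusion set" and put in a fresh one as they routinely would. It continues: "The Achilles infusion set will be placed in a provided container and biohazard bag". Then: "Participants are instructed to photograph the inflamed infusion site and contact the study staff via the provided study hotline".

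Protocol 7.1.1 lists four objective criteria for failure of an infusion set. The third is: "Signs of inflammation/infection at the infusion site including pain, erythema or induration >10 mm in diameter". If any of the four arises at home, the participant phones the 24/7 helpline to confirm the failure, inserts a new commercial catheter at another location, measures the erythema and photographs the site. On the old catheter the instruction is: "The failed CSII catheter will be left in place". Removal comes later: "The study participant will return to the study site as soon as practicable so the research staff can remove" and inspect it. There is no exception for infection.

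Two footnotes to the Schedule of Activities (Protocol 1.3) touch on the matter. Footnote 6 says that after early termination for cannula failure the "glucose clamp will not be done if failed cannula has been removed". Footnote 9 lists site evaluations at "Day 7 (or upon infusion set failure) pre-infusion set removal, post-infusion set removal".

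**The concern.** One event, a suspected infection at the site during home wear, falls under both sections, and they say opposite things about the old cannula. Followed as written, 7.1.1 keeps a cannula in a possibly infected site until a visit with no stated time limit. It also sets aside the response to infection that 2.3.3 relies on when it argues that the risk of extended wear is acceptable. Followed as written, 2.3.3 takes the cannula out before staff can see it in place, which 7.1.1 is set up to let them do. Either way, the participant departs from one section of the protocol.

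**Working it through.** The protocol gives no figure to reproduce, so the check is a comparison of text.

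**Side by side, suspected infection at home**

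| Step | Protocol 2.3.3 | Protocol 7.1.1 |
|---|---|---|
| Trigger | Evidence of infection at the site | Signs of inflammation/infection (criterion 3) |
| Contact staff | Yes, hotline | Yes, 24/7 helpline |
| Photograph the site | Yes | Yes, and measure erythema |
| Fresh set | Yes | Yes, commercial set at another location |
| Old cannula | Participant removes it; Achilles set is bagged | Stays in place |
| Who withdraws it | Participant, at home | Research staff, at a later visit |

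The first four rows agree or overlap. The last two cannot both be met. The triggers are worded differently, but an infection at the site meets both. The bagging sentence in 2.3.3 names Achilles only, whereas 7.1.1 covers both sets, so the overlap certainly includes the investigational device.

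**Does anything else settle it?**

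- *Home kit (Protocol 6.1.1.9).* It holds a cap for the set, which fits leaving it in, and a container with biohazard bag, which fits taking it out. Both are listed for use on failure.
- *Device warning (Protocol 4.1.3).* An inflamed site calls for a replacement set at a new site. That leans towards removal but does not say when the old cannula comes out.
- *Footnote 6.* It allows for the cannula having been removed but does not say by whom.
- *Footnote 9.* It expects an evaluation before removal but does not say that staff must make it.
- *Precedence.* None is stated.

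**Frequency.** Protocol 2.3.1 rates clinically significant site infection or inflammation as very rare, and still rare with extended wear. The steel-versus-Teflon trial described in Protocol 2.2.3 had 4% of sets removed for infection. Taking all wear weeks as the base (an assumption), 0.04 × (38 + 39) = 0.04 × 77 = 3.08 sets. On the 80 possible wear periods mentioned in 2.3.3, 0.04 × 80 = 3.2. Either way that is about 3 sets. Those were different devices from the two studied here, so this indicates only that such cases are few and is not a projection. The documents give no infection rate for Achilles or Silhouette, and the extra dwell time under 7.1.1 cannot be computed.

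**Effect on the analysis.** SAP 4.3.2.7.1 counts evidence of site infection as infusion set failure, whoever withdraws the cannula. SAP 4.2.6 treats the study set as removed once the participant switches to another set, even if the study set is used again. The choice of rule therefore changes neither the failure count nor the end of the wear period.

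**The case against.** The strongest reply is that the practical difference is small. Insulin delivery moves to a fresh set under both sections, staff are contacted under both, and in 7.1.1 the participant confirms the failure with staff by phone, so a clinician can advise on the old cannula. The Statement of Compliance permits departures to eliminate an immediate hazard. All of this stands, and it is why the point is minor. It does not remove the contradiction: the hazard clause permits a departure but does not tell a participant at home what to do.

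A second reply is that 2.3.3 is the specific rule and 7.1.1 the general one. That reading is possible. But 7.1.1 is the operational section, names infection itself and applies its procedure to every criterion, so helpline staff could reasonably follow it instead.

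Third, participants act on written instructions and staff on a removal SOP, and neither is among the documents. A reader might infer that participants were in fact told to leave an infected cannula in. The documents do not support that; it is unknown which rule they were given.

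A reader might also infer from footnote 6 that a clamp could be run through a failed cannula left in place, so that the rule affects the primary data. SAP 4.2.6 stands against this, because it treats the set as removed from the switch onwards.

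Finally, it is tempting to have participants remove the set for infection but leave it in for inflammation alone. Criterion 3 merges the two, and 2.3.3 itself describes the infected site as inflamed. No test is given by which a participant could separate them at home, so a clinician has to make that judgement.

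**Conclusion.** The two sections conflict for a suspected infection at home, and nothing in the protocol or SAP says which governs. That much rests on the text alone and is secure.

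It is a minor, low-frequency participant-safety inconsistency. What remains open is who withdraws the cannula and when. It has no bearing on sample size, error rates, endpoints or the handling of data. A reader might infer a serious safety failing or a threat to the trial's results, but the shared safeguards and SAP 4.2.6 rule out reading it that strongly.

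The judgement that cases would be few assumes that the protocol's own rating of infection as rare is right. The cited trial of other devices is context only.

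**What to change.** Add an exception to Protocol 7.1.1 for both sets. When criterion 3 is met at home, the participant:

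1. calls the helpline;
2. measures the erythema and photographs the site with the set still in place;
3. unless the helpline clinician judges that infection is not suspected, removes the set into the supplied container and biohazard bag;
4. inserts a new commercial set at another location;
5. returns to the study site as soon as practicable.

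Keep leave-in-place for criteria 1, 2 and 4 (unresponsive hyperglycaemia, fasting hyperglycaemia with raised ketones, occlusion alarm). Align 2.3.3, the removal SOP and the participant instructions with this rule, and have the sponsor's clinicians confirm it.

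The cost is a few sentences in the protocol and matching text in the other documents. The ruler, container and bag are already in the home kit. The real loss is that staff no longer see the cannula in situ in those cases, so the pre-removal evaluation in footnote 9 would rest on the participant's measurement and photograph. The bagged cannula can still be inspected. Visits, sample size and analysis do not change.

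SAP 2.5 records that the sponsor ended the study after the seventh participant completed, so the rule should be carried into any follow-on protocol.
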